2 OBJECTIVE

2.1 Primary Objective

The objective of this study is to compare the safety and efficacy of HBM9036 (HL036) 0.25% ophthalmic solutions with placebo for the treatment of the signs and symptoms of dry eye.

The primary objective is to evaluate the efficacy of 8-week continuous treatment with HBM9036 (HL036) ophthalmic solution (BID) in Chinese patients with dry eye and provide evidences for the Phase III trial.

2.2 Secondary Objective

The secondary objective is to evaluate the safety of 8-week continuous treatment with HBM9036 (HL036) ophthalmic solution (BID) in Chinese patients with dry eye.

3 STUDY ENDPOINTS

3.1 Primary Efficacy Endpoint

- Changes from baseline in change from pre- to post-CAE ICS score of the study eye evaluated at Visit 6 (Day 57, Week 8) according to Ora Calibra[®] Corneal and Conjunctival Fluorescein Staining Scale

3.2 Secondary Efficacy Endpoints

- Changes from baseline in change from pre- to post-CAE ICS score of the study eye evaluated at Visit 5 using Ora Calibra[®] Corneal and Conjunctival Fluorescein Staining Scale
- Changes from baseline in pre-CAE ocular discomfort of the study eye evaluated at Visit 6 according to Ora Calibra[®] Ocular Discomfort Scale
- Changes from baseline in pre-CAE ocular discomfort of the study eye evaluated at Visit 5 according to Ora Calibra[®] Ocular Discomfort Scale
- Changes from baseline in pre-CAE symptom score evaluated at Visit 6 according to Ora Calibra[®] Ocular Discomfort and 4-Symptom Questionnaire
- Changes from baseline in pre-CAE symptom score evaluated at Visit 5 according to Ora Calibra[®] Ocular Discomfort and 4-Symptom Questionnaire
- Changes from baseline in post-CAE TFBUT[®] of the study eye evaluated at Visit 6
- Changes from baseline in post-CAE conjunctival redness score of the study eye evaluated at Visit 6 according to Ora Calibra[®] Conjunctival Redness Scale
- Changes from baseline in Schirmer's test (nonanesthetized) results at Visit 6
- Change from baseline in OSDI[®] scores at Visit 6
- Changes from baseline in pre-CAE burning sensation score evaluated at Visit 6 according to Visual Analogue Scale (VAS)
- Changes from baseline in average weekly burning sensation score in subject diary at Week 8

3.3 Safety Evaluation

- Incidence and severity of ocular AEs
- Incidence and severity of non-ocular AEs

- BCVA at each visit
- Slit-lamp bio-microscopic results at each visit
- Evaluation of tolerance (at Visit 2) by Ora Calibra[®] Drop Comfort Scale and Ora Calibra[®] Drop Comfort Questionnaire
- Intraocular pressure (at Visits 1 and 6)
- Fundus photography (at Visits 1 and 6)

4 INVESTIGATIONAL PLAN

4.1 Overall Study Design and Plan

This study is a multicenter, randomized, double-blinded placebo-controlled, parallel-group Phase II study. Subjects will be randomized at Visit 2 to one of following treatment groups:

- HBM9036 (HL036) 0.25% Ophthalmic Solution
- Placebo

Subjects will receive either HBM9036 (HL036) Ophthalmic Solution (0.25%) or placebo solution as topical ophthalmic drops administered bilaterally BID. Subjects, Sponsor, and site personnel will be masked to treatment assignment.

[figure not shown]
Controlled adverse environment (CAE) is an environmental chamber used to improve the accuracy for measuring signs and symptoms (such as corneal staining and ocular discomfort) of dry eye by regulating indoor humidity, temperature, air flow and visual tasks. The introduction of CAE[®] can improve the accuracy of predicting the efficacy of the investigational product by fewer patients, fewer study sites and less time. This environmental chamber has a reliable record of use under conditions of standard test design.

During the screening period, 90-minute exposures to the CAE[®] (at Visits 1 and 2, two times) will be conducted to ascertain eligibility to enter the study by assessing the change of signs and symptoms during the 90-minute period and post-CAE exposure. Those who qualify will be randomized to receive study drug in a double-blinded manner for 56 days. Subjects will self-administer drops twice daily and will complete daily diary assessments.

At Visits 1, 2, 5 (Day 29), and 6 (Day 57), CAE[®] exposure will occur, with pre-CAE[®], during CAE[®] (symptoms only) and post-CAE[®] assessments of ocular signs and symptoms. At Visits 3 and 4, no CAE[®] exposure will occur but signs and symptoms will be assessed.

The total number of expected participants, including screen failures, is approximately 200 subjects. A total of 100 subjects are expected to be randomized.

A study flow chart appears below:

Visit 6 (Day 57 ±3): 8-Week CAE[®] Follow-up and Study Exit	Collection of Study Drug/Diary Medical/Medication Update: AE Query Urine Pregnancy Testing (as needed) Symptom Questionnaire, Visual Acuity Eye evaluations before entering the CAE [®] CAE [®] Exposure Post-CAE [®] Eye Evaluations Safety Assessments (IOP and Fundus Color Photography) Study Exit
---	--

Subjects who terminate early during the treatment period will be asked to complete safety assessments prior to commencement of any alternative dry eye therapy.

4.2 Rationale of Study Design

The expectation of this study is to observe that compared with the placebo, HBM9036 (HL036) 0.25% Ophthalmic Solution can significantly improve the tolerance of dry eye patients to environment, which is consistent with the results from the Phase II clinical trial conducted in the US. The primary endpoint of this study is:

- Changes from baseline in change from pre- to post-CAE[®] ICS score evaluated at Visit 6 according to Ora Calibra[®] Corneal and Conjunctival Fluorescein Staining Scale

Considering the mechanism of action, a randomized, double-blinded, parallel-group study design will be used. Details are provided in Section 9.2.

4.3 Rationale of Dose/Regimen and Duration of Treatment

Ocular topical administration is the best route of administration for dry eye treatment. The proposed 8-week treatment period is also based on the results from non-clinical studies, current clinical study data and the anti-inflammatory mechanism of action.

5 SELECTION OF STUDY POPULATION AND WITHDRAWAL CRITERIA

5.1 Inclusion Criteria

Individuals eligible to participate in this study must meet all of the following criteria:

1. Provide written informed consent;
2. Be at least 18 years of age at Visit 1;
3. Have a patient-reported history of dry eye for ≥ 6 months prior to enrollment;
4. Have a history of use eye drops for dry eye symptoms within 6 months of Visit 1 or desire to use eye drops;
5. Have a best corrected visual acuity of 0.7 logMAR or better (Snellen equivalent score of 20/100 or better) in each eye at Visit 1;
6. Report in the study eye a score of ≥ 2 according to the Ora Calibra[®] Ocular Discomfort and 4-Symptom Questionnaire in at least one of the dry eye symptoms at Visits 1 and 2;
7. Have in the study eye a Schirmer's Test score of ≤ 10 mm and ≥ 1 mm at Visits 1 and 2;
8. Have at least in the study eye a corneal fluorescein staining score of ≥ 2 for at least one subregion (inferior cornea, superior cornea or central cornea) according to the Ora Calibra[®] Corneal and Conjunctival Fluorescein Staining Scale at Visits 1 and 2;
9. Have at least in the study eye a conjunctival redness score ≥ 1 according to the Ora Calibra[®] Conjunctival Redness for Dry Eye Scale at Visits 1 and 2;
10. Demonstrate in the study eye a response to the CAE[®] at Visits 1 and 2 as defined by:
 - a) Having at least a ≥ 1 point increase in fluorescein staining in the inferior region in at least the study eye following CAE[®] exposure;
 - b) Reporting an Ocular Discomfort score ≥ 3 at 2 or more consecutive time points in at least the study eye during CAE[®] exposure (if a subject has an Ocular Discomfort rating of 3 at time = 0 for an eye, he/she must report an Ocular Discomfort rating of 4 for two consecutive measurements for that eye). Note: a subject cannot have an Ocular Discomfort score of 4 at time = 0);
11. Be willing and can adjust current treatment for dry eye according to the protocol, judged by the Investigator;
12. Must be willing to complete all study assessments required by the protocol.

5.2 Exclusion Criteria

Individuals who meet any of the following exclusion criteria will not be eligible to participate in the study:

1. Have any clinically significant slit lamp findings at Visit 1 that may include active blepharitis, lid margin inflammation or active ocular allergies that require therapeutic treatment, and/or in the opinion of the investigator may interfere with study parameters; have meibomian gland dysfunction requiring local or systemic treatment with antibiotics;
2. Be diagnosed with an ongoing ocular infection (bacterial, viral, or fungal), or active ocular inflammation at Visit 1;
3. Be diagnosed with Sjogren's syndrome, Steven-Johnson syndrome, or dry eye secondary to chronic graft-versus-host disease;
4. Have worn contact lenses within 7 days of Visit 1 or anticipate using contact lenses during the study;
5. Have previously had laser-assisted in situ keratomileusis (LASIK) surgery within the last 12 months, or had femtosecond small incision lenticule extraction (SMILE) within the last 12 months, or had phacoemulsification within the last 3 months, or had dry eye or aggravation of dry eye caused by other ocular operations has not been stable;
6. Have any planned ocular and/or lid surgeries over the study period;
7. Be using or anticipate using temporary punctal plugs during the study, or anticipate having permanent punctal occlusion, or have used permanent punctal occlusion and had complications such as extrusion or shifting;
8. Have used ophthalmic cyclosporine A, tacrolimus or Xiidra[®] within 60 days prior to Visit 1;
9. Be currently taking any topical ophthalmic prescription (including medications for glaucoma) or over-the-counter (OTC) solutions, artificial tears, gels or scrubs, and cannot discontinue these medications for the duration of the study (excluding medications allowed during the study); the respective wash-out periods are required for the following medications, otherwise the subjects will be excluded:
 - a) Antihistamines (including ocular): 72 hours prior to Visit 1
 - b) Oral aspirin or aspirin-containing products allowed if dose has been stable over past 30 days prior to Visit 1 and no change in dose anticipated during the study period

- c) Corticosteroids or mast cell stabilizers (including ocular): 14 days prior to Visit 1
 - d) Any medication (oral or topical) known to cause ocular drying that has not been administered as a stable dose for at least 30 days prior to Visit 1 and during the study
 - e) All other topical ophthalmic preparations (including artificial tear substitutes) other than the study drops: 72 hours prior to Visit 1
10. Be a woman who is pregnant, nursing or planning to be pregnant, or be a woman of childbearing potential who is not using an acceptable means of birth control;
 11. Be a man who does not take one or more acceptable contraceptive methods;
 12. Have severe cardiovascular diseases, liver diseases, nervous system diseases and malignant tumors, or other diseases that the Investigator believes may interfere significantly with the subject's participation in the study and follow-up, or may cause diseases leading to hospitalization during the study;
 13. Drug allergy: patients who are allergic to drugs similar to study drugs or excipients of study drugs;
 14. Drug abuse: subjects who have obvious alcohol and drug abuse judged by the Investigator;
 15. Have other remarkable diseases, traumas, or other conditions except for dry eye, which the Investigator feels may put the subject at significant risk, may confound the study results, or may interfere significantly with the subject's participation in the study;
 16. Have connection with the study sites: investigators, sub-investigators, study coordinators or employers of investigators, or direct relatives of those listed above cannot participate in the study;
 17. Cannot provide valid informed consent: have mental disorders, mental retardation, bad intentions or a history of other illnesses that limit the validity of informed consent in this study;
 18. Study drugs or devices: have used an investigational drug or device within 30 days of Visit 1 (screening) or 5 half-lives, whichever longest.

Note: subjects who participate in an observational study (i.e. no change in treatment or no other interventions is required) are not excluded.

5.3 Subject Identification

At screening visit (Visit 1), each subject will be assigned a unique screening number. All screening numbers will be assigned in strict numerical sequence at a site and no numbers will be skipped or omitted. If all inclusion criteria are met and no exclusion criteria are met at Visits 1 and 2, each subject will then be assigned a randomization number at the end of Visit 2 and block randomization will be conducted by IWRS system.

All the subjects, the Sponsor, and investigators will not know the treatment assigned to each subject and will be masked throughout the study.

5.4 Previous, Concomitant and Prohibited Medications

The use of any prescription or over-the-counter medications within 30 days before Visit 1 is to be recorded on the previous/concomitant page in electronic case report form (eCRF). Any increase or decrease in drugs or dosage change during the study should also be recorded on eCRF. Any drugs currently in use, including OTC medications and Chinese herbal medicines, are permitted if they are not prohibited in the protocol and are approved by investigators. Subjects will be told that they should contact investigators in case of any disease occurring.

All concomitant medications used during the study and their indications, doses, route of administration and dates of administration will be recorded on the concomitant page in eCRF.

5.4.1 Other Medications for the Treatment of Dry Eye

Other medications for the treatment of dry eye other than the study drugs are not permitted during the study.

5.4.2 Prohibited Medications

Prohibited medications/treatments during the study are outlined in the exclusion criteria (Section 5.2).

5.4.3 Other Prohibited Medications

Not applicable.

5.5 Other Restrictions, Illicit Drugs or Drug Abuse

5.5.1 Illicit Drugs

See the exclusion criteria for details (Section 5.2).

5.5.2 Dietary Restriction

There is no dietary restriction in this study.

5.6 Reasons for Discontinuation of Treatment or Study Withdrawal

Subjects may withdraw their consent to participate in the study at any time. The Investigator must withdraw from the study any subject who requests to be withdrawn. A subject's participation in the study may be discontinued at any time at the discretion of the Investigator and/or Sponsor and in accordance with his/her clinical judgment. When possible, the tests and evaluations listed for the termination visit should be carried out.

The Investigator must notify the Sponsor of all subject withdrawals as soon as possible. The Sponsor also reserves the right to terminate the study at any time for either clinical or administrative reasons and to discontinue participation of the individual Investigator or study site for slow enrollment or noncompliance.

Reasons for which the Investigator may withdraw a subject from the study include, but are not limited to, the following:

- Subject experiences a serious or intolerable AE;
- Subject requires medication prohibited by the protocol;
- Subject does not adhere to study requirements specified in the protocol;
- Subject was erroneously admitted into the study or does not meet entry criteria;
- Subject is lost to follow-up;
- Subject becomes pregnant;
- Death;
- Investigator's decision;
- Termination of the study by the sponsor;
- Subject's willingness.

If a subject fails to return for scheduled visits, efforts must be made to determine the reason. If the subject cannot be reached by telephone after two attempts, he will be discontinued from the study. The date of last visit will be recorded in the study records and CRF. For subjects who are reached again after lost to follow-up and have missed the visit, supplementary medications should be provided as soon as possible for them to continue the study.

If a female subject is pregnant during the study, she should withdraw from the study and be followed up until childbirth or pregnancy outcome.

5.7 Removal of Subjects from Treatment or Assessment

5.7.1 Removal of Individual Subjects

Subjects who meet any of the following criteria will withdraw from the trial:

- Withdraw the ICF for any reason;
- No longer able to continue to participate in the study for medical reasons (e.g. pregnancy, surgery, AEs or other diseases);
- Administrative reasons (protocol violation, lack of compliance);
- Harbour BioMed decides to terminate the trial early for one or all subjects (previous positive benefit-risk assessment is not supported by new toxicological findings or SAEs).

Subjects should not be discontinued from the trial due to protocol violations before discussion with the clinical research associate.

The data of the subjects who discontinue from the study before enrollment will be recorded in the study database and listed. The data of the subjects who discontinue from the study after enrollment must be recorded, and the reasons must be recorded in the source documents as well as in eCRF. These data must be included in the study database and be reported.

The procedures after early withdrawal from the trial are presented in Section 8.2.

Pregnancy

If a subject is pregnant during the study, the study drug needs to be discontinued, and the subject should be followed up until childbirth or termination of pregnancy. The data of the subject until completion of the last visit will be collected and reported in the clinical trial report (CTR); and any subsequent events will be reported in the Drug Safety Database of Harbour BioMed. Detailed information about reporting of the pregnancy events is presented in Section 7.2.9.

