8 STUDY PLAN

8.1 Schedule of Study

See Table 1.

Table 1. Schedule of Study

Procedure	Visit 1 Day -13 ± 2		Visit 2 Day 1		Visit 3 Day 8 ± 1	Visit 4 Day 15 ± 2	Visit 5 Day 29 ± 2		Visit 6 Day 57 ± 3		EOT ⁴	FU ²
	Before CAE	After CAE	Before CAE	After CAE	No CAE	No CAE	Before CAE	After CAE	Before CAE	After CAE		
Informed consent	X											
Medical/medication history and demographics	X											
Medical/Medication history update			X		X	X	X		X			
Placebo run-in dispensation		X										
Placebo run-in collection			X									
Randomization				X								
Study drug dispensation				X		X		X				
Study drug instillation				X	X							
Study drug collection					X	X	X		X		X	
Diary dispensation		X		X	X	X		X				
Diary collection			X		X	X	X		X		X	
Review of inclusion/exclusion criteria	X	X	X	X								
Adverse event Query	X	X	X	X	X	X	X	X	X	X	X	X
Urine pregnancy test	X ¹								X ¹		X ¹	
Drop tolerance assessment				X								
Ora Calibra® Ocular Discomfort Scale	X	X	X	X	X	X	X	X	X	X		
Ora Calibra® Ocular Discomfort and 4-Symptom Questionnaire	X	X	X	X	X	X	X	X	X	X		
VAS Discomfort Scale	X	X	X	X	X	X	X	X	X	X		

Procedure	Visit 1 Day -13 ± 2		Visit 2 Day 1		Visit 3 Day 8 ± 1	Visit 4 Day 15 ± 2	Visit 5 Day 29 ± 2		Visit 6 Day 57 ± 3		EOT ⁴	FU ²
	Before CAE	After CAE	Before CAE	After CAE	No CAE	No CAE	Before CAE	After CAE	Before CAE	After CAE		
OSDI [®] Questionnaire	X		X		X	X	X		X			
Visual acuity (ETDRS)	X		X		X	X	X		X		X	
Slit-lamp bio-microscopy	X	X	X	X	X	X	X	X	X	X	X	
Conjunctival redness	X	X	X	X	X	X	X	X	X	X		
TFBUT	X	X	X	X	X	X	X	X	X	X		
Fluorescein staining	X	X	X	X		X	X	X	X	X		
CAE exposure	X		X				X		X			
Discomfort grading during CAE exposure	X		X				X		X			
Schirmer's test		X		X		X		X		X		
Intraocular pressure		X								X	X	
Fundus color photography ³		X								X	X	
Subject withdrawal from the study										X		

EOT: End of Treatment

1. Applies to females of child bearing potential. See the definition for details.
2. A telephone follow-up will be made 7 days after the last dose of study drugs to collect safety information. See Section 8.4 for details.
3. If retinopathy is detected, or if it is impossible to take clear photos of both optic discs and macula lutea simultaneously, the indirect ophthalmoscope or preset lens should be inspected under the pupil dilation conditions.
4. The examination that a subject who withdraws the study must receive. See Section 8.3 for details.

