8.1.9 Visit 5: Day 29±2

Before entering the CAE

- Subject diary/study drug collection. Subject diaries and all used study drug vials dispensed for Days 15 to 29 should be collected and reviewed by a trained study technician.
- Site staff must confirm subjects have not administered their morning study drug dose at home.
- Monitoring and query of AEs
- Record all changes in concomitant medications
- Ora Calibra[®] Ocular Discomfort Scale
- Ora Calibra[®] Ocular Discomfort and 4-Symptom Questionnaire
- VAS discomfort scale
- OSDI
- BCVA Utilizing an ETDRS Chart
- Slit lamp biomicroscopy
- Conjunctival redness
- TFBUT
- Corneal staining (fluorescein)

CAE

- During the CAE[®] exposure, ODS will be collected at time 0 and every 5 minutes thereafter throughout the 90 ±5 minutes.

After leaving the CAE

- Ora Calibra® Ocular Discomfort Scale
- Ora Calibra® Ocular Discomfort and 4-Symptom Questionnaire Ocular Discomfort Score
- VAS discomfort scale
- Slit lamp biomicroscopy
- Conjunctival redness
- TFBUT
- Corneal staining (fluorescein);
- Schirmer's test;
- Monitoring and query of AEs
- Study Drug Diary/Study Drug Dispensation Prior to discharge from the study site on Visit 5 (Day 29), subjects will be educated in study drug diary recording and self-administration of study drug. Subjects will receive their assigned study drug kit with sufficient supply to last until Visit 6 and will be instructed to not self-administer study drug on the morning of their next scheduled study visit (Visit 6, Day 57).
- Schedule next visit. Subjects will be scheduled for Visit 6.

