8.2 Discontinuation of Treatment and Premature Withdrawal from Study

Subjects may be discontinued before their completion of the study due to:

- Adverse events;
- Unblinding when medically necessary;
- Protocol violations;
- Administrative reasons (e.g., inability to continue, lost to follow up);
- Termination of study by sponsor;
- Subject choice (e.g. Withdrawal of consent); and
- Other.

Note: In addition, any subject may be discontinued for any sound medical reason at the discretion of the Investigator.

Notification of a subject discontinuation and the reason for discontinuation will be made to the Sponsor and will be clearly documented on the eCRF.

Subjects who discontinue treatment should switch to proper maintenance treatment at the discretion of the Investigator. For subjects who discontinue treatment and do not finish at least one post-treatment data collection, a telephone follow-up should be made at least 7 days after the last dose of study drug.

Discontinued subjects will not be replaced.

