8.3 Unscheduled Visits and End of Treatment/Study Exit Visit

Repeat assessments, if needed, will be captured in unscheduled visits.

End of treatment/study exit visits will be captured as unscheduled visits. At least the following procedures will be completed at these visits:

- Record AEs and SAEs (if any);

- Review concomitant medications;
- Urine samples will be collected from women of childbearing potential for pregnancy tests;
- All the study drugs/subject diaries will be collected;
- Subjects will resume pre-study treatment or receive appropriate medication treatment;
- Subjects will be told to report all the SAEs that occur within 7 days after the last dose of study drug;
- Collect the reasons for discontinuation of study. These visits may be made to ensure safety of subjects. All the procedures performed at unscheduled visits must be recorded in the source documents and the eCRF page for unscheduled visits. For any procedure indicated in the eCRF, "unperformed" should be indicated if they have not been performed;
- Assessment that may be performed at unscheduled visits:
 1. Slit-lamp biomicroscopy;
 2. Visual acuity;
 3. Intraocular pressure;
 4. Urine pregnancy test;
 5. Fundus color photography or mydriasis fundus examination;
 6. Any other assessment needed in the judgement of the Investigator.

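### Protocol 5.7.1 words removal for protocol violation or lack of compliance as mandatory, and a removed subject would normally have no observed Day 57 primary endpoint, which modestly weakens the FAS analyses

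*Protocol*

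**What the plan says.** **Removal.** Protocol 5.7.1 opens its list with "Subjects who meet any of the following criteria will withdraw from the trial". One entry reads "Administrative reasons (protocol violation, lack of compliance" (closing bracket omitted). A later sentence adds: "Subjects should not be discontinued from the trial due to protocol violations before discussion with the clinical research associate". It does not mention lack of compliance.

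**Same subject matter elsewhere.**
- Protocol 5.6 is permissive: "Reasons for which the Investigator may withdraw a subject from the study include, but are not limited to, the following". Its list includes failure to adhere to study requirements.
- Protocol 8.2 is also permissive: "Subjects may be discontinued before their completion of the study due to". Its list names protocol violations but not lack of compliance.
- SAP 5.2.2 has a deviation recorded when compliance falls outside 80% to 125%, and says nothing of withdrawal.

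**After removal.** Protocol 8.3 introduces the exit procedures with "At least the following procedures will be completed at these visits". Table 1, in its note on the EOT column, calls them "The examination that a subject who withdraws the study must receive". Neither place lists CAE exposure or fluorescein staining. Section 8.3 does leave any other assessment to the investigator's judgement. Protocol 4.1 asks early terminators for safety assessments.

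**Analysis.** Protocol 9.5.1.1 names LOCF on the FAS as the primary analysis. SAP 6.2.2 puts the primary analysis on the PPS and uses FAS LOCF and a FAS MMRM (Visits 5 and 6) as sensitivity analyses. Under its LOCF rule, baseline stands in when Visits 5 and 6 are both missing.

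**The concern.** An investigator who reads 5.7.1 literally takes a non-compliant subject out of the trial. One who reads 5.6 may keep the same subject in. The protocol supports both.

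The primary endpoint is a change across a CAE exposure, and after baseline the CAE is run only at Visits 5 and 6. Removal before Visit 6 therefore normally ends any prospect of an observed Day 57 value, and analysis cannot recover it later.

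Violators and poor compliers are the subjects who separate the FAS from the PPS. If their observed outcomes are replaced by zero change, an earlier value or nothing, the FAS says less about whether the PPS result survives in everyone randomized and treated. Where 9.5.1.1 governs, the loss falls on the primary analysis itself.

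**Working it through.** **1. What each analysis holds for a removed subject**

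Compliance can be judged at Visits 3, 4 and 5, when diaries and study drug are collected. At Visit 5 this comes before the CAE: "all used study drug vials dispensed for Days 15 to 29 should be collected and reviewed by a trained study technician" is among the pre-CAE steps in Protocol 8.1.9.

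| Removal | FAS LOCF at Day 57 | FAS MMRM |
|---|---|---|
| Before the Visit 5 CAE | baseline, so zero change | no post-baseline record |
| After the Visit 5 CAE, before Visit 6 | Visit 5 change | Visit 5 record only |

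**2. The plan's own figure**

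Inputs from Protocol 9.2 and SAP 1.4: 50 randomized and 40 completers per arm, SD 0.7, and a Go threshold of -0.3 on the SAP's sign convention.

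SE = 0.7 × √(2/40) = 0.1565. At a true difference of -0.4, P(estimate ≤ -0.3) = Φ(0.1/0.1565) = 73.9%, against 74.8% in the documents. All 15 cells of the table agree within 1 percentage point. The sizing is not in question.

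**3. FAS LOCF, equal removal in both arms**

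Assumptions: k = 1 to 4 of 50 per arm removed before the Visit 5 CAE; true difference -0.4 in everyone else; f is the share of that effect the removed subjects would have shown; other dropouts set aside.

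- SE = 0.7 × √(2/50) = 0.140
- Kept to Day 57: mean difference = -0.4 × [(50 - k) + f × k]/50
- Removed: mean difference = -0.4 × (50 - k)/50
- Probability = Φ((-0.3 - mean)/0.140)

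| k per arm | Removed: mean, probability | Kept, f = 0.5: mean, probability | Fall |
|---|---|---|---|
| 1 | -0.392, 74.4% | -0.396, 75.4% | 1.0 |
| 2 | -0.384, 72.6% | -0.392, 74.4% | 1.8 |
| 3 | -0.376, 70.6% | -0.388, 73.5% | 2.9 |
| 4 | -0.368, 68.6% | -0.384, 72.6% | 4.0 |

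With f = 0 the kept and removed means coincide and nothing is lost. With f = 1, the upper bound, the kept probability is 76.2%, so the fall is 1.8 points (k = 1) to 7.6 points (k = 4). Adding the zeros barely alters the SD: with a within-arm mean change of 0.65 it runs from 0.699 (k = 1) to 0.694 (k = 4), so 0.7 is kept.

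**4. FAS LOCF, unequal removal**

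Protocol 9.2 gives a mean change of about 0.65 without saying which arm or sign. Taking 0.65 as the size of the within-arm change, each extra zero-change subject in one arm moves that arm's mean by 0.65/50 = 0.013. A gap of 1 to 4 subjects moves the difference by 0.013 to 0.052, in either direction. The pending band, from -0.3 to -0.1, is 0.2 wide.

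**5. PPS**

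Major deviators are excluded anyway, so nothing changes for them. Nor does anything change if the removals fall within the 20% dropout allowance. Otherwise, going from 40 to 36 per arm takes Φ(0.1/SE) from 73.9% to 72.8%, a fall of 1.1 points.

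All of these are normal approximations.

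**The case against.** The strongest reply is that 5.7.1, read with the rest, does not work as an automatic removal rule. The entry is a category of reason with no trigger attached. Violations must first be discussed with the clinical research associate. Protocol 9.1 provides for dropping a violator's data from a given time point onward, and SAP 5.2.2 summarizes under- and over-compliance; both contemplate such subjects staying in. This stands in part. It shows that removal is not the only outcome the authors had in mind. It does not change the wording of 5.7.1, and the discussion sentence delays removal for violations only.

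Three further objections are sound as limits:
- Section 8.2 does not name lack of compliance, so on that ground the conflict is with 5.6 alone.
- An exit CAE is unplanned but not barred. By the SAP 2.1 windows, a value at Day 43 or later would count as Visit 6.
- Zero change and the absence of exit staining come from the LOCF rule and the exit schedule, which affect every early dropout. The wording of 5.7.1 adds only its own subset, and the MMRM has no zero-change dilution.

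A reader might also infer that compliance outside 80% to 125% triggers removal. No section says so: Protocol 6.7 uses the range to define good compliance, and SAP 5.2.2 uses it to record a deviation.

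**Conclusion.** The point holds as a modest one. Section 5.7.1 is mandatory where 5.6 (non-adherence) and 8.2 (protocol violations) are discretionary, and following it normally costs the observed Day 57 endpoint.

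The cost falls on the FAS analyses: about 1 to 4 percentage points in the chance of a FAS LOCF estimate of -0.3 or better. That rests on 1 to 4 removals per arm before the Visit 5 CAE, a true difference of -0.4, SD 0.7 and half the effect in those subjects. The loss is nil if they would have shown no effect. The removal rate is an assumption, since the documents give none. Removal after Visit 5 does not cause this zero-change dilution.

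A reader might infer that the SAP's primary result is compromised. The documents do not support that: the SAP's primary analysis is on the PPS, where the effect is nil to about 1 point. The FAS figures bear on a primary analysis only if Protocol 9.5.1.1 is followed. Protocol 9.1 itself names the PPS for the main analysis, and that disagreement is a separate matter.

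**What to change.** In Protocol 5.7.1:
1. Change *will* to *may* for the administrative-reasons entry, in line with 5.6 and 8.2.
2. Extend the sentence on discussion with the clinical research associate to lack of compliance.
3. Add a sentence saying that a protocol deviation or non-compliance does not by itself end scheduled assessments through Visit 6, and that consent withdrawal and safety removals are unaffected.

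PPS membership is then settled at the review before database lock, as Protocol 9.1 and SAP 2.3 already provide. The exit visit need not change.

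The cost is one word and two sentences of text, with no new procedures. The downside is that a few non-adherent subjects continue with scheduled visits, including 90-minute CAE exposures at Visits 5 and 6.
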